8.1 Endpoint efficacy analyses

- Patient flow participant flow through the trial will be summarised using the CONSORT diagram and will reflect numbers of patients screened, consented, randomised, receiving intervention, and completed outcomes.
- Patient recruitment and retention rates we will calculate the ratio of the number of patients screened
 : recruited and time to achievement of patient recruitment target by each centre.
- 3. Acceptability of trial methods to patients and clinicians.
- 4. Fidelity of blinding we will calculate the proportion of correct guesses of patient assignment by patients and research staff at each follow up.
- 5. Delivery of co-interventions we will assess the consistency of CPP and acupuncture delivery across the three centres. Details of therapy received by each patient will be collected as part of the clinical research form at each follow up visit.

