1.2.1. Facet-joint injections

Method. A spinal needle will be placed within the facet-joint under fluoroscopic guidance, and 0.5ml 0.5% bupivacaine with 20mg methylprednisolone injected per joint. Four facet-joints will be injected, at two bilateral lumbar levels.

Notes. No more than four facet-joints will be injected to avoid any potential confounding effect attributable to the systemic action of exceeding 80mg methylprednisolone. The volume of injectate will not exceed 1ml per joint, as it is possible to rupture the intra-articular capsule with volumes of greater than 1ml, spreading the local anaesthetic and steroid to other potential pain-generating structures.

Identification of facet-joints. The facet-joints are paired synovial joints between the superior and inferior processes of the vertebrae at each level of the spine. They are load-bearing joints and are easily identifiable on radiographic imaging such as X-rays. The patient will attend the day surgery unit at their respective trial centre. The procedure is carried out in the prone position, with the back exposed. The investigator will examine the patient's back to elicit para-spinal tenderness of the lumbar facet-joints – these are the joints to be injected and the spinal level will be identified using image intensification (the C-arm can be rotated obliquely to facilitate this). A spinal needle (e.g. 22G 90mm Quinke) will be advanced through skin, subcutaneous tissues and paraspinal muscle, towards the facet-joint under X-ray guidance. Entry of the needle into the facet-joint will be confirmed by injection of radio-opaque contrast and visualisation of the needle position within the joint space, and local anaesthetic and steroid will be injected into the facet-joint.

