1.2.2. Sham procedure

Method. A spinal needle will be placed in the peri-articular space surrounding the facet-joint under fluoroscopic guidance, at each of the four painful areas at two bilateral lumbar levels. Normal saline (0.9% sodium chloride) 0.5ml will be injected through each needle.

Notes. Para-spinal tenderness will be elicited as before (section 5.5.1), and the needle inserted under fluoroscopic guidance to confirm placement in the peri-articular space. A small volume of normal saline will be injected away from the joint capsule, to avoid irritation of any structure that is part of the facet-joints, including the fibrous capsule, synovial membrane, hyaline cartilage, and bone. The sham group will not receive systemic steroid administration, as it has been shown that the addition of parenteral steroid makes no contribution to the pain relief achieved by targeted

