2.2. Trial objectives

Specific objectives of this feasibility study are:

1. To assess the eligibility criteria, recruitment and retention of patients in the two treatment arms (FJI versus sham procedure).

- a. by assessing the feasibility of recruitment in the three centres, with regards to a
 potential definitive trial, by reviewing the number of completed patient data sets,
 auditing the quality of data entry at the centres, assessing and analysing any protocol
 violations (such as failure to deliver the combined physical and psychological
 programme), side effects and other adverse outcomes.
- 2. To assess the feasibility and acceptability of the two treatment arms from the point of view of patients and their pain teams.
- 3. To assess the feasibility of the proposed definitive trial design including:
 - a. Testing of randomisation and blinding procedures.
 - b. Development of an appropriate active and sham procedure for FJIs.
 - c. Assessment of the consistency of the trial sites to deliver the combined physical and psychological programme.
 - d. Ability to collect the outcomes proposed for the main trial (pain, functioning, health-related quality of life, anxiety and depression, health care resource utilisation, complications, and adverse events).
- 4. To estimate outcome standard deviation to inform the power calculation for a definitive trial.
- 5. To finalise the protocol design, statistical plan, number of centres required and study duration of the definitive trial.

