3.4 Diagnostic test

Method. Diagnostic medial branch nerve blocks will be carried out at each painful level with fluoroscopic guidance, using a spinal needle to inject 0.5ml 1% lidocaine per level.

A positive response is defined as a 50% or greater pain reduction lasting for over 30 minutes (i.e. the duration of action of lidocaine).

The rationale for carrying out diagnostic medial branch nerve blocks is because of their safety, simplicity and prognostic value⁹. A volume of 0.5ml has been associated with a lower incidence of inadvertent injectate spread¹⁴. The rate of false positives is most often cited between 15 and 40%, due to factors such as placebo response, use of sedation, and excessive use of local anaesthesia. We will aim to

minimise this by not using sedation and by limiting the local anaesthetic volume to 0.5ml per nerve block. There is currently no justification for double, comparative blocks as these are associated with a significant false-negative rate and are not shown to be cost-effective¹⁵.

4. Investigational Medicinal Product

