5.5 Schedule of treatment for each visit

Barts Health NHS Trust

Participants for the study will be sent an invitation letter and information leaflet and will be asked to contact the study centre if they are interested in taking part. They will be screened for eligibility by telephone or in person and then provided with the consent forms to consider their participation. They will have as long as they need to make an informed decision and will be able to discuss their participation prior to their appointment with the study staff. Primary and secondary outcomes will be collected at 4 time points: baseline (pre-randomisation), and at 6 weeks, 3 months and 6 months post-randomisation. In addition, patient demographic data (e.g. age, gender, duration of chronic pain) will collected at baseline. Data will be collected by an independent member of the research team, blinded to patient allocation.

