5.6 Schedule of assessment

Visit 1 Screening and informed consent. Outcome questionnaires at baseline.

- Visit 2 Diagnostic test.
- Visit 3 FJIs or sham procedure.
- Visit 4 Outcome questionnaires at 6 weeks.
- Visit 5 Outcome questionnaires at 3 months.
- Visit 6 Outcome questionnaires at 6 months.

There will be 6 study visits in total -3 visits are part of routine clinical practice (patients are seen in the pain clinic, referred for FJIs, then followed-up at 6 to 8 weeks), and 3 visits are additional. We anticipate that it will take up to one hour to complete the set of outcome questionnaires. The outcome questionnaire visits will take place in a research nurse-led clinics.

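### Treatment guesses are first taken at 6 weeks with no reason recorded, so the blinding check cannot separate a detectable sham from patients inferring their arm from pain relief

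*Protocol*

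**What the plan says.** Among the objectives in section 2.2, item 3a is "Testing of randomisation and blinding procedures" and item 3b is the development of a suitable active and sham procedure. Section 2.1 makes the test-run of the sham one of the conditions for calling the definitive trial feasible. Section 1.1 describes the sham as a novel approach, designed because no validated one was available.

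The measure is in section 8.1, item 4: "we will calculate the proportion of correct guesses of patient assignment by patients and research staff at each follow up". Section 5.5 sets the outcome time points as "baseline (pre-randomisation), and at 6 weeks, 3 months and 6 months post-randomisation". In section 5.6 the treatment visit reads only "Visit 3 FJIs or sham procedure", and the next contact is "Visit 4 Outcome questionnaires at 6 weeks". The list of evaluations in section 5.8 includes satisfaction after treatment, but neither a treatment guess nor a reason for one.

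The arms differ in what is injected. The active arm receives "0.5ml 0.5% bupivacaine with 20mg methylprednisolone injected per joint" (section 1.2.1). For the sham, section 1.2.2 states: "Normal saline (0.9% sodium chloride) 0.5ml will be injected through each needle". Every randomised patient has already responded to a lidocaine block, under this definition in section 3.4: "A positive response is defined as a 50% or greater pain reduction lasting for over 30 minutes".

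**The concern.** Whether the sham is convincing is decided largely on the day, when the patient experiences the procedure. The plan first asks about it around six weeks later, when the patient also knows whether the pain has improved. Someone who feels better has grounds to guess active, and someone who does not has grounds to guess sham, even if nothing about the procedure gave the arm away. If the treatment works, correct guesses then exceed chance without any fault in the sham.

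There is also a threat particular to this design. Patients come to Visit 3 with recent experience of relief from a local anaesthetic, and only the active injection contains one. Whether its presence or absence reveals the arm that day is a natural question about this sham, and the protocol specifies nothing that would record it.

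At stake is how far one of the study's main products can be interpreted: evidence on whether this sham can be carried into the definitive trial. The timing and content of the question are matters of data collection, so a later analysis plan cannot recover an answer that was never asked for.

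**Working it through.** **Inputs.** All come from section 8.2 unless stated: 60 randomised equally to two arms; 20% attrition, with a maximum of 1 in 3 given later in the same section; a 2-point difference on the 0–10 pain scale; SD 3.0 to 4.0. The guess times are from sections 5.5 and 8.1.

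**The plan's own figure.** Completers per arm: 60 × (1 − 0.20) / 2 = 24. This reproduces. With 1 in 3 lost it is 60 × (2/3) / 2 = 20. Section 8.1 gives no figure for the blinding item itself.

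**Correct guesses from outcome alone, with a perfect sham.** Assumptions of this check, not of the protocol: improvement is normal with the same SD in both arms, the quoted SD applies to improvement, and every patient guesses active if improvement exceeds the midpoint between the two arm means. Then, in either arm,

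P(correct) = Φ(difference / (2 × SD)).

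| Difference | SD 3 | SD 4 |
|---|---|---|
| 0 | 50.0% | 50.0% |
| 1 | 56.6% | 55.0% |
| 2 (protocol) | Φ(2/6) = 63.1% | Φ(2/8) = 59.9% |
| 3 | 69.1% | 64.6% |

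If only half of patients guess this way and the rest at random, the protocol's difference gives 0.5 × 63.1 + 0.5 × 50 = about 57%, or 0.5 × 59.9 + 0.5 × 50 = about 55%.

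**True unblinding that looks the same.** If a fraction u know their arm and the rest guess at random, P(correct) = u + (1 − u)/2, so u = 2P − 1. For 63.1% this is 0.26, and for 59.9% it is 0.20. A concealed sham with a working treatment and a sham that reveals the arm to a fifth or a quarter of patients therefore give the same result.

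**Precision.** The 95% half-width at 50% correct is 1.96 × √(0.25/n).

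| Patients answering | Per arm | Both arms together |
|---|---|---|
| All 60 | n = 30: ±18 points | n = 60: ±13 points |
| 48 (20% lost) | n = 24: ±20 points | n = 48: ±14 points |
| 40 (1 in 3 lost) | n = 20: ±22 points | n = 40: ±15.5 points |

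An observed 30/48 (62.5%) has a Wilson 95% interval of 48% to 75%. That is compatible with chance, with guessing from outcome and with partial unblinding.

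**Why report by arm.** If 80% of patients in each arm guess active, correct guesses are 80% in the active arm and 20% in the sham arm. The overall figure is (80 + 20)/2 = 50% and looks like chance, although most sham patients believe they had the active injection.

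**The case against.** The strongest reply is that an early guess is not clean either. Just after the procedure, bupivacaine against saline may be at its most noticeable, so a correct guess at Visit 3 may reflect the drug rather than a poor sham. Later guesses have their own value, because beliefs held when pain is self-reported can bias the outcome. This stands. It is why the early guess should sit beside the later ones rather than replace them or be declared the main result, and why the reason should be recorded.

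It can also be said that the case report form is a separate document (section 9.3), and that the list in section 5.8 omits the treatment guess even at follow-up, where section 8.1 requires it. Silence in that list therefore proves little. That is fair, but section 8.1 itself ties the guess to follow-up, and the protocol nowhere asks for an earlier one.

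A reader might infer more than the text supports:

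- **That the proportion is pooled over arms.** Section 8.1 does not say so. A by-arm split, the handling of don't-know answers and a formal blinding index may all be in the analysis plan, which is not shown; their absence here is no fault.
- **That operators' guesses will be counted.** Section 1.2 makes operators part of the research team, so the term for staff is loose. However, guesses are taken at follow-up, which section 5.6 places in nurse-led clinics, and section 5.5 has data collected by a blinded team member. Nothing says that operators will be asked.

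**Conclusion.** The point holds as one of timing and missing information. The first guess is at 6 weeks, with no guess at or soon after the procedure and no reason recorded, so the planned measure cannot tell unblinding by the procedure from inference from pain outcome. On the protocol's own difference and SD, that inference alone could yield about 60% to 63% correct with a perfect sham. This assumes normal improvement and that every patient guesses from improvement; fewer such patients or a smaller effect bring it closer to 50%.

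A reader might conclude that the measure reflects pain outcome instead of the sham, or that an ineffective treatment would pass for good blinding. The documents do not support that. With no treatment effect, guessing from outcome adds nothing to 50%, while patients who recognised their arm would still push the proportion above it. The guess mixes two sources; it is not blind to either. The measure is therefore informative but ambiguous, and the change is a cheap improvement rather than the repair of an invalid design.

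**What to change.** 1. At Visit 3, after the procedure and before discharge, ask each patient for a guess (active, sham or don't know) and the reason for it.
2. Keep the planned follow-up guesses and record the reason there too.
3. Report the early and follow-up guesses by arm with 95% confidence intervals.
4. State in section 8.1 that staff guesses come from blinded staff only.

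The cost is one extra form item at Visit 3, a reason field at follow-up and a by-arm table. Per-arm intervals will be wide, about ±18 points with 30 per arm and ±20 with 24, so the results will describe the blinding rather than prove it. The early guess can still reflect immediate anaesthetic relief; the recorded reason helps to interpret this but does not remove it. The change has to be in place before the first procedure, since the answers cannot be collected afterwards.

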8.2 Sample size

Barts Health NHS

NHS Trust

We will recruit a total of 60 patients and randomly and equally allocate them to either intervention and control groups. Assuming a 20% attrition rate, we have 24 complete data sets per arm at the end of the study. This sample size will allow us to achieve our various feasibility objectives. For example, 60 patients gives the ability to estimate the precision of our assumed attrition rate with error of error of ±5% at 95% confidence level and 24 patients per arm is acceptable for a reasonable estimate of variance of outcomes²⁰. To predict the sample size for the main trial we have made the following assumptions for the pain intensity scores: for a pain NRS (0-10), IMMPACT propose a clinically important minimal difference of 2 points³. Based on a typical pain NRS standard deviation of 3.0 to 4.0 seen in previous chronic pain trials, at 90% power and 5% alpha, a two-arm superiority trial would require a total of 100 to 160 complete patient data sets. From 1000 new patient attendances at the pain clinics with low back pain, we expect approximately 1 in 4 patients to be eligible to enter the study. This is based on our clinical experience and published studies based on responses to controlled diagnostic facet-joint injections performed in accordance with the criteria established by the International Association for the study of pain3. Of these 250 patients, approximately 60% will consent to enter the study. Following diagnostic medial branch nerve blocks, we would expect approximately 40% patients to have a positive response^{21, 22.} These 60 patients will be randomised to the two groups, with a maximum of 1 in 3 patients dropping out over study period.

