8.5 Statistical analysis

As this is a feasibility study, we do not propose to formally inferentially test differences in outcomes or costs between or within the groups. Recruitment and attrition rates will be calculated with 95% confidence intervals. We shall report mean and standard deviations for primary and secondary outcomes for the two groups at baseline and all follow-up visits.

9. Data Handling & Record Keeping

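### Section 8.2 claims ±5% precision for attrition at 95% confidence; 60 patients at 20% attrition give about ±10 percentage points.

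*Protocol*

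**What the plan says.** Protocol section 8.2 sets the size of the study: "We will recruit a total of 60 patients and randomly and equally allocate them". It then turns assumed dropout into completers: "Assuming a 20% attrition rate, we have 24 complete data sets per arm at the end of the study". It claims that "This sample size will allow us to achieve our various feasibility objectives" and offers two examples. One is that 60 patients estimate the "assumed attrition rate with error of error of ±5% at 95% confidence level". The other is that "24 patients per arm is acceptable for a reasonable estimate of variance of outcomes". The section ends by allowing for heavier loss, "with a maximum of 1 in 3 patients dropping out over study period".

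Section 8.5, like the opening of section 8, commits to the matching analysis: "Recruitment and attrition rates will be calculated with 95% confidence intervals". Section 2.1 makes the ability to recruit and keep enough patients one of the conditions for calling the definitive trial feasible. Objective 1 in section 2.2 covers "recruitment and retention of patients in the two treatment arms".

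**The concern.** A 95% margin of ±5 points is tight for a proportion near 20% estimated from 60 people, and the arithmetic does not support it.

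The error matters because retention is a declared feasibility condition and because objective 5 uses this study to settle the number of centres and the duration of the definitive trial. A reader of section 8.2 would expect an observed 20% to mean roughly 15% to 25%. The interval that section 8.5 commits the study to report will be about twice as wide, so the results will visibly disagree with the protocol's own promise.

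**Working it through.** **Inputs, all from section 8.2:** n = 60 randomised (30 per arm); assumed attrition p = 0.20; stated precision ±5% at 95% confidence; upper attrition figure 1 in 3. The interval is taken as two-sided because the protocol writes ±.

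**The protocol's own figures**

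- Completers per arm: 60 × 0.80 / 2 = 24. This reproduces.
- Precision of ±5 points at 95%: this does not reproduce, as follows.

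**Precision at the assumed rate**

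- Standard error = sqrt(p(1 − p)/n) = sqrt(0.20 × 0.80/60) = 0.0516, or 5.2 points.
- 95% half-width = 1.96 × 0.0516 = 0.101, or 10.1 points. The normal-approximation interval is about 10% to 30%.
- For 12 dropouts in 60, the Wilson 95% interval is 11.8% to 31.8% and the exact interval is 10.8% to 32.3%.
- Ratio to the claim: 10.1/5 = 2.02.

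**What ±5 points would mean**

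- Confidence attached to ±5 points at n = 60: 2Φ(0.05/0.0516) − 1 = 0.667, about 67%.
- Number needed for ±5 points at 95%: 1.96² × 0.16/0.05² = 246.
- With n = 60, ±5 points at 95% would hold only if attrition were about 4%.

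**Other readings that might rescue the figure** (p = 0.20, 95%, unless stated)

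| Reading | Half-width (points) |
|---|---|
| One-sided limit, n = 60 | 8.5 |
| Continuity-corrected, n = 60 | 11.0 |
| 48 completers as denominator | 11.3 |
| 150 consented (250 × 60%) as denominator | 6.4 |
| Finite-population correction, N = 150 / 250 / 1000 | 7.9 / 8.8 / 9.8 |
| p = 1/3, n = 60 | 11.9 |
| One arm, n = 30 | 14.3 |

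Reading ±5% as relative to 20% would mean ±1 point, which is further away still. None of these gives ±5 points at 95%. Only a multiplier of 1 in place of 1.96 comes close, at 5.2.

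**Consequence for planning.** Section 8.2 puts the definitive trial at 100 to 160 complete data sets. Taking those figures as given and dividing by (1 − attrition):

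| Attrition range | Recruits for 100 complete | Recruits for 160 complete |
|---|---|---|
| 15% to 25% (as claimed) | 118 to 134 | 189 to 214 |
| 11.8% to 31.8% (Wilson) | 114 to 147 | 182 to 235 |

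The spread rises from 16 to 33 recruits in the first case and from 25 to 53 in the second, so the planning uncertainty due to attrition roughly doubles.

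**The case against.** The strongest defence is that little in the study turns on this number. No test, stopping rule or numerical retention threshold uses ±5%, and section 2.1 sets no attrition cut-off. Section 8.5 is correct as written and will show the true interval in the report. All of that stands. It limits the harm to misinforming readers before the results; it does not make the stated figure right.

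A reader might infer more than the documents support:

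- **That the main basis for 60 patients collapses.** The precision is introduced as an example, next to the variance argument, which the error does not touch. Sixty also agrees with the recruitment funnel in the same section: 1000 × 1/4 × 60% × 40% = 60. The claim is one of two stated reasons, though the only one with a quantified precision.
- **That the authors mistook a standard error for a 95% margin.** The match with 5.2 points suggests it, but the protocol gives no derivation, so this remains an inference.
- **That the study is too small and needs 246 patients.** That number only shows what the claimed precision would require. Nothing in the protocol says that a feasibility study needs ±5 points.
- **That 20% could not be told apart from the worst case.** For 12 of 60 the upper limit, 31.8% (Wilson) or 32.3% (exact), lies below 1 in 3, if narrowly. The protocol does not call 1 in 3 a decision threshold either.
- **That a per-arm precision was promised and missed.** Section 8.2 claims precision only for the 60 together. The ±14 points per arm is useful context for objective 1, not a second error.

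**Conclusion.** The precision stated in section 8.2 is wrong. At the assumed 20% attrition, 60 patients give a 95% half-width of about ±10.1 points, so the claim is too favourable by about a factor of two. This assumes a two-sided interval and all 60 randomised patients as the denominator; the alternatives tried do not recover ±5 points.

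The conclusion stops there. The sample size of 60, the 24 completers per arm and the planned 95% intervals are not called into question by this error. It can be settled now, because a later analysis plan cannot make the sentence true.

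**What to change.** Keep 60 patients and replace the precision statement in section 8.2 with, for example:

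> 60 randomised patients estimate an attrition rate of 20% with a 95% confidence interval of about ±10 percentage points (10% to 30%, normal approximation; 12% to 32% by the Wilson method).

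The method should be named with each range, since the Wilson interval is not centred on 20%. Optionally add that the half-width is about ±12 points if attrition reaches the section's maximum of 1 in 3, and about ±14 points within each arm at 20%.

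The cost is one sentence and a less favourable stated precision. It needs no extra patients and no change to the analysis in section 8.5.
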